### 1.9 Pre-hospital stroke trials

Two previous trials of acute stroke treatment started by paramedics in the prehospital setting in the USA or the UK have shown that enrolment and treatment of patients with acute stroke in the field is a practical and feasible strategy for phase III trials, and that the proportion of enrolled patients with stroke-mimicking conditions (and not a stroke) can be as small as 4 to 12%. In these two trials, the median intervals between stroke onset and the start of study treatment were 45 and 60 minutes, respectively. In RIGHT-2, the median time from stroke onset to randomisation was 71 minutes.

For the present study, it is essential that the proportion of enrolled patients with a stroke-mimicking condition rather than a stroke is small. We will use the Face-Arm-Speech Test (FAST), which is used as a mnemonic to increase knowledge of stroke symptoms in the general population and to support diagnosis of stroke by paramedics. The FAST has been

used in clinical practice for many years by the Dutch ambulance organisations. In a UK study, paramedics using the FAST achieved high levels of detection and diagnostic accuracy of stroke. Because patients with more severe strokes have a larger chance of occlusion of a proximal intracranial artery or intracerebral haemorrhage, and because these are the most likely to benefit from improved collateral circulation, patients should at least score 2 on the first three items of the FAST. This is also likely to increase the discriminatory power of the test, although this has not been tested.

### 1.10 Conclusion

In conclusion, there is a strong need for additional stroke treatments that can be used in a broad population of patients with acute ischaemic stroke or intracerebral haemorrhage. Very early blood pressure reduction with transdermal GTN appears a very promising option because this has shown to be safe in patients with acute ischaemic stroke or intracerebral haemorrhage; reduces blood pressure within 15 minutes of application, without a reduction in cerebral blood flow; as an NO donor, may improve cerebral collateral circulation before the start of recanalisation strategies; has been associated with time-dependent improvement of functional outcome in post-hoc analyses of previous acute stroke trials; and is cheap and easy to administer. The lack of benefit of GTN observed in RIGHT-2 may be explained by chance and does not preclude a beneficial effect in trials in a different stroke population, such as in The Netherlands, where rates of endovascular treatment are much higher. However, the tendency towards harm in specific subgroups does warrant close monitoring of safety in any future trial. Treatment with GTN in the prehospital setting has the advantage of strongly reducing the delay to treatment for a broad range of stroke patients to less than 1 hour after symptom onset, because this is simple and safe and does not require laboratory testing of the blood or imaging of the brain before the start of treatment.

## 2. OBJECTIVES

### ***Primary objective***

To assess the effect of transdermal GTN, started within 3 hours of symptom onset in the prehospital setting, on functional outcome at 90 days in patients with acute ischaemic stroke or intracerebral haemorrhage.

### ***Secondary objectives***

To assess whether the effects of transdermal GTN, started within 3 hours of symptom onset in the prehospital setting, on functional outcome at 90 days are consistent across specific subgroups of patients, i.e., those with 1. ischaemic stroke; 2. ischaemic stroke treated with endovascular techniques; or 3. intracerebral haemorrhage.

To assess the effect of GTN on collaterals, size of the ischemic core and salvageable brain tissue on admission to the hospital.

### ***Tertiary objectives***

To collect and analyse data regarding the deferred consent procedure and its association with patient recall and satisfaction at three months from randomisation.

To study the efficiency of national IAT implementation, given the availability of IAT hospitals and capacity, and travel times of ambulance services. To this end, we aim to collect data (time delays and diagnostics) from each step in the acute stroke pathway as input parameters for a simulation model. This way we can study the regional set-up of the IAT organisational model.

### 3. STUDY DESIGN

This is a multicentre, prospective randomised, open clinical trial with blinded outcome assessment (PROBE) of transdermal GTN in a dose of 5 mg/day for one day, in 1400 adult patients with suspected stroke. Patients will be recruited in a maximum of 10 ambulance regions in the Netherlands. Patients will be included in the study by a paramedic before hospital admission. Study treatment will be started in the prehospital phase, and continued in the admitting hospital. MR ASAP is part of a consortium of 5 acute stroke trials conducted by the Dutch 'Collaboration for New Treatments of Acute Stroke' (CONTRAST, see Appendix 1). The trial will be performed according to ICH-GCP principles, the Declaration of Helsinki as most recently amended in 2013, and national regulatory requirements. Because the majority of patients will be incapacitated and because the informed consent procedure should not delay the process of transporting the patient to the hospital, we will use a deferred consent procedure.

## 4. STUDY POPULATION

### 4.1 Population (base)

The study population will consist of patients aged 18 years or older, in whom the attending paramedic makes the probable diagnosis of acute stroke with a moderately severe to severe deficit.

The trial will be conducted by members of the CONTRAST consortium. Although the trials draw from the pool of patients with acute ischemic stroke, there is no competition between the endovascular treatment trials in the collaboration (Appendix 2).

### 4.2 Inclusion criteria

In order to be eligible to participate in this study, a subject must meet all of the following criteria:

1. Age 18 years or older;
2. Probable diagnosis of acute stroke, as assessed by the paramedic in the prehospital setting;
3. Score of 2 or 3 on the Face Arm Speech Test (FAST, Appendix 3);
4. Systolic blood pressure  $\geq$  140 mm Hg;
5. Possibility to start the trial treatment within 3 hours of symptom onset;
6. Intention to transport the patient to one of the participating hospitals;
7. Written informed consent (deferred).

### 4.3 Exclusion criteria

A potential subject who meets any of the following criteria will be excluded from participation in this study:

1. Considerable pre-stroke dependency in activities of daily living, defined as staying in a chronic nursing home or rehabilitation centre;
2. Known pregnancy or lactation;
3. Indication for acute treatment with nitroglycerin or known use of nitroglycerin in the previous 12 hours;
4. Known hypersensitivity to GTN, nitrates in general, or the adhesives used in the patch
5. Glasgow Coma Scale  $<$  8;
6. Known with any of the following heart disorders: myocardial insufficiency due to obstruction; aortic or mitral valve stenosis; constrictive pericarditis; hypertrophic obstructive cardiomyopathy; cardiac tamponade;
7. Known marked anaemia, defined as haemoglobin  $<$  5 mmol/L;
8. Known closed angle glaucoma;

9. Known concomitant use of phosphodiesterase type-5 inhibitors, (e.g. sildenafil, tadalafil, vardenafil).

#### 4.4 Sample size calculation

MR ASAP is powered to detect a statistically significant shift in the distribution of the scores on the mRS at 90 days in the overall study population, assuming an effect that leads to a 7% absolute risk reduction (ARR) for poor functional outcome (mRS 3 - 6) in the GTN group compared with controls (48% vs 41%). The risk of a poor functional outcome of 48% is based on findings in the Field Administration of Stroke Therapy – Magnesium (FAST-MAG) trial, a trial including 1700 patients with suspected stroke in the prehospital setting. This effect is considerably smaller than the 23% ARR observed in the small phase II trial RIGHT, with patients treated within 4 hours of stroke onset, and smaller than the 9% ARR in the subgroup of patients enrolled in ENOS within 6 hours of symptom onset. We consider a 7% ARR sufficient to change clinical practice. We assume that the use of covariate adjustment will increase statistical efficiency by 20%, which is based on the R^2 in the MR CLEAN trial data of an adjustment model containing age, pre-stroke mRS and items 4, 5a, 5b, 9 and 10 of the NIHSS that correspond to the FAST score. The sample size calculations are based on a simulation study with a proportional odds model. A total study size of 1280 patients then allows for a power of 80% to detect a difference at a 5% significance level in the scores on the mRS in patients treated with GTN as compared with controls. As we expect to include around 10% stroke mimics, in whom no treatment benefit is expected we increase this sample size with 10% and aim for inclusion of 1400 patients.

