### 10.2 Primary outcome

The primary effect estimate will be a shift in the mRS score at 90 days ( $\pm$  14 days) assessed by means of ordinal logistic regression, and will be expressed as a common odds ratio with 95% confidence interval. The assumption of proportional odds will be assessed using the likelihood ratio test. The statistical analyses will be performed according to the intention-to-treat principle and adjusted for relevant baseline characteristics including age, sex, stroke type, score on the FAST at study inclusion, time of symptom onset to randomisation, pre-stroke score on the mRS, and ambulance region.

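### The 80% power stated for 1280 patients cannot be reproduced from the inputs in section 4.4, which give about 88-90%; the error is conservative and its source cannot be identified from the protocol

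*Protocol*

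**What the plan says.** Section 4.4 sets the target: "MR ASAP is powered to detect a statistically significant shift in the distribution of the scores on the mRS at 90 days", "assuming an effect that leads to a 7% absolute risk reduction (ARR) for poor functional outcome (mRS 3 - 6) in the GTN group". The two rates are 48% in controls and 41% with GTN. On adjustment it says: "We assume that the use of covariate adjustment will increase statistical efficiency by 20" per cent. On method it says: "The sample size calculations are based on a simulation study with a proportional odds model". The result follows directly: "A total study size of 1280 patients then allows for a power of 80% to detect a difference at a 5% significance level". Stroke mimics come in only after that number: "in whom no treatment benefit is expected we increase this sample size with 10% and aim for inclusion of 1400 patients".

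Section 10.2 names the same kind of test for the primary analysis. The shift in mRS at 90 days is "assessed by means of ordinal logistic regression, and will be expressed as a common odds ratio with 95% confidence interval", adjusted for baseline characteristics.

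The protocol does not give the control mRS distribution, the allocation ratio, the sidedness of the 5% level, how the 20% enters the calculation, or whether the odds ratio in the simulation is marginal or conditional on covariates.

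**The concern.** The wording of section 4.4 makes 1280 the product of three things: the ordinal test, the 48% versus 41% effect, and the 20% gain. An ordinal test that uses all seven mRS levels is clearly more efficient than a comparison of two proportions. A further 20% gain should bring the requirement well below 1280.

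The number matters because 1400 is built on it by adding 10%. If the printed power is wrong, a reader cannot tell how much margin 1400 has against a weaker covariate gain or more mimics than the assumed 10% (section 1.8 reports 26% in RIGHT-2). The effect detectable with 80% power would also be smaller than the 7 points stated.

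**Working it through.** **Inputs.** From section 4.4: 48% versus 41% with mRS 3-6; 20% efficiency gain; 1280 patients; 80% power; 5% level. Assumed, because not stated: 1:1 allocation, two-sided test, and a control mRS distribution with 48% in categories 3-6. Several distributions were tried.

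**Common odds ratio.** (0.48/0.52)/(0.41/0.59) = 1.328, so ln OR = 0.2839 and its square is 0.0806.

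**Ordinal sample size (Whitehead formula).** N = 12 (z_a + z_b)² / [(ln OR)² × (1 − Σp³)], where p is the category proportion averaged over the two arms. For 80% power, (1.960 + 0.842)² = 7.849.

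Worked example: control proportions for mRS 0 to 6 of 0.14, 0.20, 0.18, 0.14, 0.12, 0.06 and 0.16. Applying the odds ratio gives 41% with mRS 3-6 in the GTN arm and 1 − Σp³ = 0.973.

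- No gain: N = 12 × 7.849 / (0.0806 × 0.973) = about 1201.
- Gain as N × 0.8: about 960.
- Gain as N / 1.2: about 1000.

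Four plausible distributions together give 1198-1213, 958-971 and 998-1011 respectively.

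**Power at 1280.** Power = Φ(√[N_eff × (ln OR)² × (1 − Σp³) / 12] − 1.960). In the worked example:

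| Use of the 20% gain | Effective N | Calculation | Power |
|---|---|---|---|
| None | 1280 | Φ(2.893 − 1.960) | 82.5% |
| N × 1.2 | 1536 | Φ(3.169 − 1.960) | 88.7% |
| N / 0.8 | 1600 | Φ(3.234 − 1.960) | 89.9% |

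A tie-corrected rank-test simulation (40,000 runs) gave 82.4%, 88.6% and 89.8%. A simulation of adjusted proportional odds regression at 1280 (700 runs, marginal effect 48% versus 41%, observed relative efficiency 1.21) gave 91%.

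**Does the missing mRS distribution explain the gap?** A very concentrated distribution (42% at mRS 1, 35% dead) still gives 85-87%. To reach exactly 80%, 1 − Σp³ would have to be 0.761 (effective N 1536) or 0.730 (effective N 1600). An outcome with only two categories gives 1 − 0.555³ − 0.445³ = 0.741. The mRS would therefore have to behave almost as a binary outcome. An almost two-point distribution (50% at mRS 1, 45% dead) gives 81-82%.

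**Other unstated choices.** A one-sided test would raise the power further. A 2:1 allocation would still give about 85-86%.

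**Calculations that do land near 1280.**

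| Route | Result | Printed item it contradicts |
|---|---|---|
| Dichotomised 48% vs 41%, 80% power, N = 1582 | × 0.8 = 1266; / 1.2 = 1318 | Test |
| Ordinal at 90% power, N about 1604-1607 for two of the spread-out distributions | × 0.8 = about 1283-1286 | Power |
| Ordinal, no covariate gain | about 82% power at 1280 | Gain |
| OR 1.33 entered as a covariate-conditional effect | about 81-84% power at 1280 | Risk difference (marginal about 6 points, not 7) |
| Effect already diluted by 10% for mimics (ln OR × 0.9), with gain | 81-83% power at 1280 | Mimics added only after 1280 |

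**Detectable effect.** With 1280 patients and the gain, the risk difference detectable with 80% power is about 6.1-6.2 points for plausible mRS distributions.

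**The case against.** The strongest objection is that section 4.4 does not say whether the odds ratio of 1.33 was the marginal or the covariate-conditional coefficient in the simulation. With a conditional log odds ratio of 0.2839, adjusted proportional odds regression at 1280 (1500 runs per setting) gave 81%, 84% and 82% power for covariate standard deviations of 0.8, 0.9 and 1.0 on the logit scale, with efficiency ratios of 1.24, 1.29 and 1.36. The test and roughly the stated gain are then kept, and 80% is nearly right. This stands as a possible origin. It does not remove the inconsistency, because the marginal risk difference then falls to about 5.8-6.2 points, while section 4.4 prints 48% versus 41%.

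A reader might also infer that 1280 came from a dichotomised comparison reduced by 20%, so that section 4.4 describes a different test from section 10.2, or that either the test or the covariate gain named in section 4.4 was not used. The documents do not support either inference. Both sections name ordinal regression, and an ordinal calculation at 90% power times 0.8 fits about as well as the binary one. On that route, test and gain are as stated and only the printed power is wrong.

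Nor can 80% be called strictly impossible. With the gain as N × 0.8, a two-category outcome would need about 1577 × 0.8 = 1262 patients, within 1.4% of 1280. With the gain as N / 1.2, a nearly binary scale would reach 80%. What can be said is that no realistic seven-level mRS distribution does so.

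It is also fair that the simulation details could sit in a separate report, and that neither enrolment nor the analysis depends on the correction. The printed power, however, stands beside inputs that do not produce it.

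**Conclusion.** The point holds as a failure to reproduce. With 48% versus 41% as a marginal effect, a proportional odds test and the 20% gain, 80% power needs about 960-1010 patients and 1280 gives about 88-90%. The printed figure is about 8-10 percentage points too low for plausible mRS distributions and about 5-7 points too low for a very concentrated one. This rests on 1:1 allocation, a two-sided 5% level and assumed mRS distributions.

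The error is conservative on the printed inputs. A reader might take it to mean that the trial is underpowered; that does not follow. How 1280 was obtained cannot be settled from the protocol. The candidates have different consequences: a misprinted power, an unused covariate gain, a smaller target effect, a different test, or mimics allowed for twice.

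**What to change.** Rerun the simulation and correct whichever of the printed items is wrong (power, sample size, risk difference, gain or test) so that section 4.4 agrees with itself. If the inputs stand as printed, the sentence would say that 1280 patients give about 88-90% power for the adjusted ordinal analysis.

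Section 4.4 should also state:

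- the control mRS distribution used;
- the allocation ratio and whether the 5% level is two-sided;
- whether the odds ratio is marginal or conditional on covariates;
- how the 20% enters (N × 0.8 or N / 1.2);
- whether the effect had already been diluted for mimics before the 10% was added.

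Keep the target of 1400 and restate its power for the primary ordinal analysis. As a guide, with ln OR reduced by 10% for mimics, 1400 patients with the gain give about 85-86%.

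The cost is a short simulation and a reworded paragraph. Enrolment, procedures and the primary analysis do not change.

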The phase III randomised Rapid Intervention With Glyceryl Trinitrate in Hypertensive Stroke Trial-2 (RIGHT-2) was based on the promising findings in the studies above. RIGHT-2 randomised 1149 adults with presumed stroke within 4 hours of onset who had a face-arm-speech test score of 2 or 3 and systolic blood pressure of 120 mm Hg or higher to transdermal GTN (5 mg once daily for 4 days) or a similar sham dressing. Treatment was started in the ambulance by paramedics, with treatment continued in hospital. The median time to randomisation was 71 min (IQR, 45 to 116). 597 (52%) patients had ischaemic stroke, 145 (13%) had intracerebral haemorrhage, 109 (9%) had transient ischaemic attack, and 297 (26%) had a non-stroke mimic at the final diagnosis of the index event. In the GTN group, participants' systolic blood pressure was lowered by 5.8 mm Hg compared with the sham group ( $p < 0.0001$ ), and diastolic blood pressure was lowered by 2.6 mm Hg ( $p = 0.0026$ ) at hospital admission. Early administration of GTN did not have an effect on functional outcome in patients with a final diagnosis of stroke or transient ischaemic stroke (adjusted common odds ratio for poor outcome (acOR), 1.25; 95% CI, 0.97 to 1.60;  $p = 0.083$ ), nor in the complete population (acOR, 1.04; 95% CI, 0.84 to 1.29;  $p = 0.69$ ). There was also no

difference in the risk of death at 90 days (19% vs 17%; acOR, 1.11; 95% CI, 0.84 to 1.47;  $p = 0.47$ ) or in the risk of serious adverse events. Remarkably, GTN was associated with an improved functional outcome in patients with a stroke mimic (acOR, 0.54; 95% CI, 0.34 to 0.85;  $p=0.0081$ ). This positive finding was not localised to any particular type of mimic. In subgroup analysis, a tendency towards harm of GTN in RIGHT-2 was seen in patients with intracerebral haemorrhage, very early stroke (<1 h), and severe stroke. Furthermore, patients with intracerebral haemorrhage treated with GTN had larger haematoma size and more mass effect on hospital admission.

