## 10. STATISTICAL ANALYSIS

### 10.1 Statistical analysis plan (SAP)

The analysis and reporting of the trial will be in accordance with CONSORT guidelines. Before follow-up will have been completed, a statistical analysis plan (SAP) will be developed that will specify: (i) Hypotheses to be tested; (ii) Treatment effects to be estimated in order to satisfy the primary and secondary objectives of this trial; (iii) Technical description of the statistical methodology and procedures for performing the statistical analysis of outcome measures and SAE data; (iv) Primary, secondary, and sensitivity analyses; and (v) Subgroup analyses. The SAP will be signed off by the trial Executive Committee and then uploaded on the public area of the trial website. The final statistical analysis will be performed once recruitment has ceased, final follow-up has been completed, final data have been checked and any errors corrected, and the database has been locked.

All analyses will be performed according to the intention-to-treat principle. Baseline data by treatment allocation will be reported with statistical procedures. Missing values for baseline characteristics will be reported. Missing baseline characteristics will be imputed using regression imputation.

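### The 10% top-up for stroke mimics in section 4.4 suits patients left out of the analysis, not no-effect patients kept in it under intention-to-treat

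*Protocol*

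**What the plan says.** Section 4.4 aims to detect a "shift in the distribution of the scores on the mRS at 90 days in the overall study population", assuming a fall in poor outcome (mRS 3 to 6) from 48% to 41%. After allowing for a 20% efficiency gain from covariate adjustment it states: "A total study size of 1280 patients then allows for a power of 80% to detect a difference at a 5% significance level". It then adds: "As we expect to include around 10% stroke mimics, in whom no treatment benefit is expected we increase this sample size with 10" per cent, which leads to 1400. The 80% is attached to 1280; that 1400 preserves it is implied.

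On who is analysed, section 10.1 says "All analyses will be performed according to the intention-to-treat principle", and section 10.2 repeats the principle for the primary outcome. Section 5.1 provides for removing the patch when a patient proves not to have a TIA or stroke, but not for removing that patient from the analysis. The primary objective in section 2 names only patients with ischaemic stroke or intracerebral haemorrhage.

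On the mimic rate, section 1.9 cites two prehospital trials with shares as low as 4 to 12%. For RIGHT-2, section 1.8 reports that "297 (26%) had a non-stroke mimic at the final diagnosis of the index event".

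**The concern.** The top-up sentence makes two assumptions: about one patient in ten will be a mimic, and mimics gain nothing from treatment. When such patients stay in the comparison they do more than take up places. They pull the estimated common odds ratio towards 1. Required sample size varies with the inverse square of the log odds ratio, so a simple proportional increase is too small.

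At stake is how a neutral result would be read. Someone relying on section 4.4 would take 1400 patients to give 80% power for the planned effect. If the analysis is the one in sections 10.1 and 10.2, that figure is too high on the protocol's own numbers, and power falls quickly as the mimic share rises.

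**Working it through.** **Inputs.** From section 4.4: 80% power at N = 1280, 5% significance, 48% vs 41%, 20% efficiency gain, 10% mimics with no benefit, final N 1400. From section 1.9: mimic shares of 4 to 12%. From section 1.8: 26% in RIGHT-2. Assumed because not stated: two-sided test, 1:1 allocation. The sum of the normal quantiles is 1.960 + 0.842 = 2.8016.

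**1. The plan's own figures.** 1280 x 1.10 = 1408 and 1280/0.9 = 1423; both are close to 1400. For 1280 itself, a dichotomised comparison of 48% with 41% needs 1582 in total; 1582 x 0.8 = 1266 and 1582/1.2 = 1318, both within 3% of 1280. The steps below take 1280 = 80% as given.

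**2. What the top-up achieves if mimics are excluded.** 1400 x 0.9 = 1260 patients analysed. Power = Phi(2.8016 x sqrt(1260/1280) - 1.96) = Phi(0.820) = 79.4%. For that analysis the top-up is essentially adequate.

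**3. What is needed if mimics are kept.** With share m and no effect in mimics, the log odds ratio becomes about (1-m) times its value in stroke patients. Hence

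- required N = 1280/(1-m)^2; at m = 0.10, 1280/0.81 = about 1580;
- power at 1400 = Phi(2.8016 x (1-m) x sqrt(1400/1280) - 1.96), where 2.8016 x sqrt(1400/1280) = 2.930. At m = 0.10: Phi(2.637 - 1.96) = Phi(0.677) = 75.1%.

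| Mimic share | N for 80%, mimics kept | Power at 1400, mimics kept | Power at 1400, mimics excluded |
|---|---|---|---|
| 4% | 1389 | 80.3% | 81.9% |
| 10% | 1581 | 75.1% | 79.4% |
| 12% | 1653 | 73.2% | 78.5% |
| 26% | 2338 | 58.2% | 71.2% |

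The break-even share for 80% at 1400 solves (1-m)^2 = 1280/1400, so 1-m = 0.956 and m is about 4.4%.

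**4. Check of the approximation.** The mixed population was simulated with a rank test (40,000 runs), with the effect calibrated so that 1280 gives 80%. Mimics had either the same mRS distribution as control stroke patients or a milder one. Power at 1400 was about 75% at 10% mimics, 72 to 73% at 12% and 57 to 58% at 26%.

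**5. Dependence on 1280.** The control mRS distribution is not given, so five assumed distributions with 48% in mRS 3 to 6 were tried. The proportional-odds formula is N = 12 x 2.8016^2 / [(log OR)^2 x (1 - sum of cubed category shares)]. Here OR = (0.48/0.52)/(0.41/0.59) = 1.328, log OR = 0.284, and the last bracket ranges from 0.937 to 0.975. This gives 1198 to 1247 unadjusted, or 958 to 998 after multiplying by 0.8. Power at 1400 with mimics kept is then:

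- with the full 20% gain: 85 to 86% at 10% mimics, 69 to 71% at 26%;
- with no gain: 76 to 78% at 10% mimics, 59 to 61% at 26%.

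**The case against.** **The analysis population is not settled.** The primary objective is confined to stroke patients, and the statistical analysis plan is not at hand. If it excludes mimics, the top-up is about right at 10%. This stands, and it is why the finding is conditional. But the protocol text on analysis says intention-to-treat in the overall population.

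**The 7% reduction may already be the all-comer effect.** Section 4.4 refers to the overall study population and takes its 48% from a trial in suspected stroke. On that reading dilution is already built in, no top-up is needed, and 1400 gives Phi(2.930 - 1.96) = 83.4%. The top-up sentence does not fit this reading, because it treats 1280 as patients who can benefit. Section 4.4 cannot mean both.

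Three stronger inferences are tempting and not supported:

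- *That the protocol contradicts its own 10%.* It does not; 10% lies within the 4 to 12% of section 1.9. RIGHT-2 shared the ambulance setting and a FAST score of 2 or 3, but it enrolled at systolic pressure of 120 mm Hg or higher within 4 hours, against 140 mm Hg and 3 hours here. The documents do not show that its 26% carries over.
- *That 1280 is wrong.* Section 4.4 says it came from a simulation, and neither the mRS distribution nor the way the 20% gain was applied is given. The figure can be queried but not shown to be an error. If the ordinal base really were 958 to 998, the shortfall at 10% mimics would disappear (step 5).
- *That 26% mimics brings power below 80% whatever is done.* This holds on the calibrations above only while mimics stay in the analysis. With them excluded, 1036 patients against a base of 958 to 998 give 81 to 83%.

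**Conclusion.** The point holds in conditional form. The adjustment in section 4.4 does not match the analysis that the protocol describes. Taking 80% at 1280 as given, with mimics analysed and unaffected by treatment, the implied 80% at 1400 is about 75% at the planned 10% and 73% at the top of the cited range. At about 4% mimics the target is met. The 58% at 26% mimics is a sensitivity result, not a forecast for this trial.

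The shortfall of about five points at 10% rests on accepting 1280, on mimics staying in the primary analysis, and on the 7% reduction referring to stroke patients. Changing any one of these can remove it. The protocol leaves the last two unclear, and that is itself part of what needs correcting.

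**What to change.** Keep 1400 and rewrite the end of section 4.4:

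1. State whether mimics are in the primary analysis, reconciling the primary objective in section 2 with the intention-to-treat statements in 10.1 and 10.2. State also whether the 7% reduction applies to stroke patients or to everyone randomised.
2. If mimics stay in and the 7% refers to stroke patients, replace the 10% increase with 1/(1-m)^2 and restate the power at 1400.
3. Show that power for mimic shares from 4% to 26%.

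Separately, ask the sponsor for the control mRS distribution behind 1280 and how the 20% gain was applied, so that the base figure can be checked.

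The cost is a rewording and a less favourable stated power. No extra patients are required.
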